4.5. Quality Control

Quality assurance of testing will begin with a clearly documented staff training programme. A register of staff who have been trained, and their competence assessed will be maintained, and only staff whose names appear on this list will be permitted to undertake testing. Staff will also receive regular update training, and periodic reassessment of their competence.

4.6. Serious and unexpected adverse events

There are no foreseeable risks of mortality or significant morbidity associated with testing. Every effort will be made to minimise any risk through training. All **serious adverse events*** believed to be associated with the study should be reported by fax to the Study Office as soon as possible. This report should be followed within 2 weeks by a completed SAE form.

4.7. Other management at discretion of local doctors

All other aspects of patient management are entirely at the discretion of the local doctors. Mother and child are managed in whatever way appears best for them, with no special treatments and no extra follow-up visits.

5. OUTCOME MEASURES

5.1. Protection from bias

There are many possible sources of bias in accuracy studies (20) and these have recently been highlighted in the STARD statement (21). Selection bias may arise if the sample is not suitably representative of the population. This is likely to occur with use of non-consecutive or convenience sampling. The study will seek to recruit all consecutive eligible newborns. A related issue is that of spectrum bias whereby the accuracy of tests varies among study samples with differences in disease spectrum i.e. prevalence of CHD. It is possible that centres that perform fetal echocardiography may diagnose more newborns antenatally, thus affecting the spectrum composition. Information on PO testing and clinical examination of symptomatic newborns with suspected CHD will be collected and those newborns that were antenatally diagnosed to have CHD. Sensitivity analysis will explore the variation in test accuracy due to spectrum composition.

The PO testing procedure will be standardised in the first phase of the study and criteria for interpretation and thresholds have been determined *a priori* (7).

The use of different reference standards for test positive and test negative cases is not ideal but this is the most practicable way to verify presence or absence of disease. Empirical studies have shown that studies with differential verification produce more biased estimates of accuracy than studies with complete verification by the preferred reference standard, particularly when differential verification is not pre-specified in the design or completely at random. The direction and magnitude of bias is likely to depend on whether differential verification will lead to different detection rates of CHD under different reference standards. If complete verification by the preferred reference is not possible and different reference standards have to be used, the best approach is to incorporate differential verification in the design (22), the approach used in this study. With this design, the estimates of positive and negative predictive values under the two reference standards, the key parameters for decision analytic modelling, will escape any bias or interpretive problems. The estimates of sensitivity and specificity will also escape any

* For the purposes of this study, "serious" adverse events are those occurring in either subjects or testers which are fatal, life-threatening, disabling or require some form of medical or surgical treatment.

difficulties in interpretation as the focus will be only on clinically significant CHD which is likely to be detected equally well by both reference standards.

One of the conclusions that arose from the recent systematic review is the need for a large well conducted study, aimed at improving the precision of the sensitivity estimate of the test. The sensitivity of PO as a screening test for CHD varied between 25% (95% CI, 13% to 41%) (12) and 98.5% (95% CI, 91.8% to 100%) (15) in previously conducted studies. The performance of the test, particularly estimates of sensitivity depends on the absolute number of patients with disease. Thus there is imprecision of the sensitivity estimates due to the low prevalence of CHD in relatively small studies. This study has been planned to be large enough to achieve good precision, as shown in section 6.1.

5.2. Primary outcome measures

These will be the accuracy of each index tests for detection of CHD, expressed as sensitivity, specificity, positive and negative predictive values and positive and negative likelihood ratios, together with 95% confidence intervals.

5.3. Secondary outcome measures

5.3.1 Clinical Examination

The presence or absence of irregularities in heart rate, rhythm and sounds or murmurs and suspicion of cyanosis observed through clinical examination will be noted. The date, time and grade of person performing the test will be recorded.

5.3.2 Assessment of patient acceptability

We define acceptability broadly in this study to incorporate the psychological impact of screening on parents. We will examine acceptability of pulse oximetry to parents using a structured questionnaire. The questionnaire will be designed specifically for the study incorporating standardised measures as appropriate. It will be administered as soon as is practicable after testing to limit recall bias whilst being sensitive to the distress of parents. As far as possible, the questionnaires will be administered before mother and baby are discharged. Otherwise, if appropriate, the questionnaire will be sent to the mother by post. Mothers will not be approached until the local clinician/midwife feels it is appropriate and face to face or telephone interviews will be offered as appropriate. Mother's address and telephone number will be collected as necessary.

Parents of all babies who screen positive, i.e. all true positive and false positive cases, will receive the questionnaire or a structured interview based on the questionnaire. All parents of children with CHD who screen negative, i.e. the false negative cases, will also be approached at a later stage. Finally a sample of the largest group will be approached: parents whose babies do not have CHD and who screen negative, i.e. the true negative cases. The inclusion of all four groups of parents will enable the differentiation of the impact of screening *per se* from that of the outcome of screening.

In designing the questionnaire it will be important to maximise the precision and validity of the instrument. As this is not a randomised-controlled trial, no comparison across testing procedures will be carried out where maximum differences in scores would be expected. Therefore the instrument must measure acceptability as accurately as possible so that any differences between sub-groups (e.g. socio-economic, ethnic) can be discerned. In order to maximise face and content validity, preliminary focus group discussions will be held with:

- parents of children with CHD diagnosed postnatally
- experienced midwives and paediatricians
- representatives of paediatric cardiology support groups (e.g. Little Hearts Matter)

From these, a set of items will be derived which will seem relevant to the participants and cover all the areas thought to be important by participants.

Pilot testing will be carried out to make certain the questionnaire is usable. It is anticipated that the questionnaire will measure acceptability and satisfaction in the following areas:

- the procedure(s) for testing
- the information provided when consent is obtained
- processes for giving test results.

Parents will also be asked whether they would be prepared to have PO testing after future births, or recommend it to others, since these give the most reliable measures of satisfaction. In addition, comparisons will be made using all data across social, ethnic, age and parity groups to see if testing is acceptable across all groups and, if it is not, the areas where acceptability is low and negative impact is high, so that procedures may be reviewed.

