6. ACCRUAL AND ANALYSIS

6.1. Sample size

The approach used in the sample size calculations is to consider the power that a study of a certain size has for the lower limits of the confidence intervals for both sensitivity and specificity to exceed particular values (and hence prove that the test is statistically significantly superior to those values). Sample size computations have been undertaken assuming that the screening strategy will have a sensitivity of 75% and a specificity of 99.5%. Sample sizes for CHD prevalence between 2 and 5 per 1000 using a one-tailed significance level of 2.5% have been computed.

Simulations of the study design and analysis (using 10,000 repetitions) were performed to account for (1) sampling variability in the observed number of cases of CHD and (2) sampling variability in the observed sensitivity and specificity, and (3) to incorporate the use of binomial exact methods to estimate confidence intervals. Standard asymptotic sample size computations do not allow for all three of these issues to be considered simultaneously. Plots of power against the values of sensitivity and specificity that the study wishes to rule out were constructed for sample sizes of 10000, 15000, 20000, 25000, 30000 and 35000.

Based on these simulations it was observed that a sample size of 20,000 will have 80% power to demonstrate that sensitivity is above 61% at a prevalence of 5 per 1000 in the overall sample. For the subgroup of women who are not selectively screened antenatally, it is anticipated the prevalence to be around 2 per 1000, a level at which sensitivity of 52% can be detected with 80% power. If the sample size is increased to 25,000 the study will have 80% power to prove the sensitivity to be above 63% and 55% at 5 and 2 per 1000 CHD prevalences respectively; if it is increased to 30,000 the corresponding values are 64% and 57%. Variation of prevalence does not affect the power to detect differences in specificity. For sample sizes above 15,000 the study will have greater than 90% power to prove that the specificity is above 99.3%.

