Further simulations using lower assumed values of the sensitivity and specificity for the screening strategy were undertaken. Statistical power to test absolute differences in sensitivity and specificity of the same magnitude was noted to be comparable to the above scenario for assumed values are within a reasonable range of those used above. Thus a sample size of 25,000 will have 80% power to prove that sensitivity is higher than a value 12% (prevalence 5 per 1000) or 20% (prevalence of 2 per 1000) below the assumed sensitivity of the test, and the specificity is above a value 0.2% below the assumed specificity.

The assumption about disease prevalence is quite conservative. A review of 62 prevalence studies since 1955 estimated a combined prevalence of 6 per 1000 live births of moderate to severe CHD (38). If prevalence in this study is higher than 0.5%, it will have more than the projected power to undertake subgroup analyses confidently. On this basis, considering the likely prevalence, the study aims to recruit a sample of 20,000 neonates.

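### Questionnaires are sampled by screening result, but the planned comparison of acceptability across demographic groups does not condition on that result

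*Protocol*

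**What the plan says.** Protocol section 5.3.2 makes the chance of being approached depend on the screening result:

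- Screen positives: "Parents of all babies who screen positive, i.e. all true positive and false positive cases, will receive the questionnaire", or a structured interview based on it.
- False negatives: "All parents of children with CHD who screen negative, i.e. the false negative cases, will also be approached at a later stage".
- True negatives: "Finally a sample of the largest group will be approached: parents whose babies do not have CHD and who screen negative". The size of this sample and the sampling fraction are not given.

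The same section gives the reason for covering every result: "The inclusion of all four groups of parents will enable the differentiation of the impact of screening" in itself from the impact of what the screen found.

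For the demographic question it then says that "comparisons will be made using all data across social, ethnic, age and parity groups to see if testing is acceptable across all groups". The stated use is to find areas of low acceptability and high negative impact, so that procedures can be looked at again. The sentence mentions neither stratification nor adjustment by result.

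**The concern.** The pooled questionnaires are not a cross-section of screened parents. Three of the four result groups are taken in full and the fourth, by far the largest, is thinned. A comparison that pools them without regard to result mixes two things: how a demographic group feels about testing given what it was told, and how many of its respondents had a positive or missed result. Section 5.3.2 says the four groups exist to keep those two apart, but its sentence on the demographic comparison does not carry that through.

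At stake is where a review of procedures would be directed. A gap between ethnic or social groups could reflect who was sampled and who replied, not a difference in acceptability.

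**Working it through.** **Inputs from the protocol.** Section 6.1: "the study aims to recruit a sample of 20,000 neonates", "assuming that the screening strategy will have a sensitivity of 75% and a specificity of 99.5" per cent. Sections 4.3.1 and 6.1: prevalence 5 per 1000.

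**Reproducing the protocol's own figure.** Section 4.3.1 expects 9 per 1000 to go to echocardiography, with 40-50% of them having clinically significant CHD.

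- Screen-positive rate = 0.005 × 0.75 + 0.995 × 0.005 = 0.008725, or 8.7 per 1000, which rounds to 9.
- Proportion with CHD = 0.00375 / 0.008725 = 43%.

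Both agree with the protocol.

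**Expected counts at 20,000.** CHD cases: 20,000 × 0.005 = 100.

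- True positives: 100 × 0.75 = 75
- False negatives: 25
- False positives: 19,900 × 0.005 = 99.5
- True negatives: 19,800.5

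Screen positives are 174.5 (0.87% of those screened). Parents who are not true negatives number 199.5 (1.0%).

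**Composition of the questionnaires.** Let m be the number of true negatives sampled. The protocol does not give m, so a range is assumed, with full response from the other three groups. The screen-positive share is 174.5 / (199.5 + m).

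| m (assumed) | Screen-positive share | Ratio to 0.87% |
|---|---|---|
| 200 | 174.5 / 399.5 = 43.7% | 50 |
| 400 | 174.5 / 599.5 = 29.1% | 33 |
| 1,000 | 174.5 / 1,199.5 = 14.5% | 17 |
| 2,000 | 174.5 / 2,199.5 = 7.9% | 9 |

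**Route 1: the result mix differs between groups.** Assume two groups of 10,000, with acceptability 95% in true negatives and 75% in everyone else, identical in both groups. Assume false positive rates of 0.5% and 1.0%, and m/2 true negatives from each group. Parents who are not true negatives number 37.5 + 12.5 + 49.75 = 99.75 in group A and 37.5 + 12.5 + 99.5 = 149.5 in group B. Pooled acceptability in a group is 0.95 − 0.20 × k / (k + m/2), where k is that number.

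| m | Group A | Group B | Difference |
|---|---|---|---|
| 200 | 85.0% | 83.0% | 2.0 points |
| 400 | 88.3% | 86.4% | 1.9 points |
| 1,000 | 91.7% | 90.4% | 1.3 points |
| 2,000 | 93.2% | 92.4% | 0.8 points |

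In the screened population the difference is 0.20 × (149.5 − 99.75) / 10,000 = 0.1 point. Given the result, it is zero.

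**Route 2: true-negative sampling or response differs.** Keep the 95% and 75%, give both groups the same result rates, split the population 70:30, and let the smaller group's true negatives be sampled or reply at half the rate. Then k is 139.65 and 59.85, and the true negatives returned are m × 0.70/0.85 and m × 0.15/0.85.

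- m = 200: 85.8% against 82.4%, a difference of 3.4 points.
- m = 2,000: 93.4% against 92.1%, a difference of 1.3 points.

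The population difference is 0.

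**Null checks.** With equal result rates and equal true-negative sampling and response, the pooled difference is 0 at every m. If acceptability does not depend on the result, there is no distortion.

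**The case against.** The strongest reply is that naming the data to be used does not name the model. An analysis that includes every questionnaire and adjusts for result would satisfy the sentence, and a statistical analysis plan that is not at hand may say so. That is right as far as it goes. A reader might infer that the protocol commits to an unweighted, unadjusted pooled mean; the text does not say that. What stands is narrower: the protocol chose to state the analysis set for this comparison, and stated it without the conditioning that its own reason for the four groups calls for.

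Three other strong readings also go beyond the text.

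- A reader might infer that acceptability in the screened population will be understated. Section 5.3.2 plans comparisons between groups and promises no overall figure.
- A reader might infer that a spurious ethnic gap is to be expected. That needs the result mix, true-negative sampling or response to differ between groups. Section 3.2 expects acceptability and willingness to participate to vary by ethnicity, which makes differential response plausible, but nowhere says that positive rates vary.
- A reader might infer that screen-positive parents decide the pooled result. For the sample sizes considered here they are heavily over-represented but never a majority.

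The premise that acceptability depends on the result is itself uncertain. Section 5.3.2.2 reports evidence of lasting effects of false positives and also evidence against them. Views on the information given at consent may shift less than distress does.

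The artefact is also small beside sampling error. On the Route 1 assumptions the standard error of the group difference is about 3.5, 2.6 and 1.6 points for m = 200, 400 and 1,000, so the bias is 0.6 to 0.8 of one standard error. This limits the practical harm, but it does not justify leaving in a bias that a known covariate removes.

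**Conclusion.** The point holds in a limited form. Sampling by result, combined with a demographic comparison that does not condition on result, departs from the stated aim of separating the impact of screening from that of its outcome. The over-representation follows from the protocol's own figures once a true-negative sample is assumed: 0.9% of the screened population against about 44% to 8% of questionnaires for samples of 200 to 2,000.

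A misleading group difference is conditional. It needs acceptability to vary with the result and the groups to differ in result mix, true-negative sampling or response. In the false-positive-rate illustration it is 2.0 to 1.3 points for 200 to 1,000 true negatives, against 0.1 in the screened population. The 95% and 75%, the doubled false positive rate and the true-negative sample sizes are all assumptions. If the groups are alike in these respects the artefact is zero.

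This concerns a secondary outcome. The accuracy analysis is unaffected.

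**What to change.** Amend the sentence in section 5.3.2 to say that comparisons across social, ethnic, age and parity groups include every questionnaire but are stratified by screening result group, or made in a model adjusted for it. With only about 75 true positive, 100 false positive and 25 false negative families expected, adjustment will be more workable than separate strata for most demographic splits.

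If any acceptability figure is reported for the screened population, weight the true negatives by the inverse of their sampling fraction, and record that fraction.

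Result group is already known for each respondent, so no new data are needed beyond the sampling fraction. The cost is a change of wording and somewhat wider intervals for weighted estimates.

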5.3.2.1. Measuring Distress

Psychological distress will be assessed across the populations using standardised instruments, so that levels of distress can be compared to population norms and to levels measured in other screening studies. Specifically we will use:

- State anxiety form of the Spielberger State-Trait Anxiety Inventory (STAI). This instrument has been widely used and validated in a number of clinical studies on screening (23;24). It is a short, closed format questionnaire of current anxiety levels.
- Depression subscale of the Hospital Anxiety and Depression Scales (HADS). Again this instrument has been widely used and validated in clinical studies as a measure of mood, including previous screening research (23). Some of this literature has been reviewed in a systematic review (25).

In order to understand variations in acceptability and the impact of testing on distress levels, measures will also be taken of possible explanatory variables including:

- Illness perceptions of CHD which will be measured using a brief version of the Revised Illness Perceptions Questionnaire (26).
- General optimism which will be measured using the 2 item short form of the Life Orientation Test (27).

5.3.2.2. Assessment of parents who receive false positive results

The literature on antenatal and neonatal screening suggests that the effects of false positives may extend over considerable periods of time in some circumstances (28-31). In part this may be due to the information and support provided for such parents (32;33). However other work contradicts this and suggests the high levels of anxiety are dispelled by diagnostic tests showing the baby is healthy. Given the contradictions in the literature, parents receiving false positive results will be assessed after testing and at the one year follow up. This will give us an indication of both the degree and duration of distress caused by the outcome. If there is significant change over this period, a second assessment will also give a better indication of the acceptability of PO screening to this group. Given that some of the literature on false positives results suggests an impact on the parent-child bond, a parental bonding questionnaire will be administered at both time points.

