1.2. Literature review

1.2.1 Accuracy of PO as a screening test for CHD in newborns

The NHS Research and Development Health Technology Assessment Programme (HTA) commissioned a systematic review of screening for CHD in newborns which was published in 2005 (6). This report included 4 studies examining the role of PO as a screen for CHD in newborns. In 2007, we published a further systematic review of this screening test (7). An extensive search (from database inception to 2006) to retrieve primary and review articles was performed and from a total of 233 citations, 8 relevant studies - 4 more than those included in the previous HTA report (6) - were identified (Table 1). A careful and detailed analysis of the findings were summarised by meta-analysis using the bivariate model, which allows for some variation in threshold. The review can be summarised as follows:

- The quality of the studies was varied in both design and conduct: six studies recruited newborns consecutively (8-13); two were case control studies (14;15) - a

design that biases the results by overestimating the diagnostic odds ratio; two were not prospective (14;15); three studies raise concerns about spectrum bias due to exclusions of antenatally diagnosed cases (10;11;13); none calculated power *a priori*; and sample size was often inadequate to precisely estimate sensitivity.

- There were various thresholds for abnormality of test results (Table 1).
- Only one study explored the added value of PO above the accuracy achieved through clinical examination. The combination of PO and clinical examination had a sensitivity of 76.9% (95% CI, 46.2% to 95%) and specificity of 99.9% (95% CI, 99.8% to 100%) (8).
- None of the studies evaluated acceptability of testing to parents and the psychosocial impact of false positive results or identification of non critical CHD.
- None of the primary studies provided information on cost and cost effectiveness.

Table 1 The accuracy of PO for diagnosing CHD in asymptomatic newborns

Test	No. of patients	Sensitivity % (95% CI)	Specificity % (95% CI)	False Positive Rate% (95% CI)	Timing of the test after birth
Most commonly used threshold					
saturation* ≤95% foot	11281	60 (14.7-94.7)	100 (100-100)	0	After 24 hrs or discharge
saturation* ≤95% foot or hand	2114	66.7(9.4-99.2)	99.9(99.7-100)	0.1(0-0.3)	As close to discharge as possible
saturation* ≤ 95% foot	3262	96.8(73.6-100)	99.7(99.5-99.9)	0.3(0.1-0.5)	Between 6 and 12 hours

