4.3.1 Echocardiography

Echocardiography is a resource intensive procedure, and will only be undertaken on those with symptoms or signs at clinical examination (as is current practice) or those with low PO readings. Given an assumed performance of 75% sensitivity and 99.5% specificity, and an overall prevalence of 5 per 1000, in our design, we would expect 9 per 1000 to undergo echocardiography based on low saturation by PO or symptoms apparent at clinical examination and between 40-50% of these will have clinically significant CHD. Thus we anticipate between 200 and 300 extra echocardiographic examinations during the study. To enable the participating hospitals to cope with this increased demand, a specially appointed clinical research fellow will be able to visit centres to perform echocardiograms when the hospital cannot accommodate them themselves.

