If exam is normal, a second PO reading needs to be taken. This should be taken 1-2 hours after the first reading. Please complete section 7 below.

If exam is abnormal, the baby needs to be referred straight to the Neonatal team for further investigation and management. A second PO reading does not need to be taken. Please continue with sections 9-14 overleaf.

Section 7: Second Pulse Oximetry Reading

Performed in: Delivery Suite Post Natal Unit Neonatal Unit

Performed by:
PRINT NAME: _____

Doctor Nurse Midwife Midwifery Assistant Care Assistant Neonatal nurse

Date	Time	Foot sats (%)	Right hand sats (%)	% difference	Pass/Refer

*If less than 95% in either limb or ≥3% difference between limbs, this is a **Fail**, the baby needs to be referred to the Neonatal team for further investigation and management. Please continue with sections 8-14 overleaf.*

*If the result is normal (i.e. **Pass**), nothing further needs to be done. Please ensure all above sections are completed. Please put this form in the participant pack and put it in the Pulse Ox collection box.*

The following sections only need to be completed if the clinical examination found an abnormality or if the second pulse oximetry reading was a Fail and the baby has been referred to the Neonatal team for further investigation and management.

Section 8: Hyperoxia Test (only to be completed if second PO reading was a fail)

Performed by: Nurse SHO Registrar Consultant

Did saturation increase to 95% or above? Yes No

Section 9: Clinical Symptoms

If baby showed signs of CHD at birth, describe

Collapse Cyanosis Acidosis Respiratory distress

Did this baby have a respiratory illness or any illness other than CHD?

Yes No If yes details: _____

Section 10: Echocardiography

Date of echocardiography ___ / ___ / ___ Time ___ : ___ (24 Hour)

Echocardiographer: Cardiology Research Fellow Other Echocardiographer

Result: Normal Abnormal Uncertain

Details: _____

Section 11: Review of Echocardiography

Reviewed by: Cardiology Research Fellow Consultant Other

(Please tick more than one box if applicable)

Date of review ___ / ___ / ___

Result: Normal Abnormal Uncertain

Details: _____

If there is a *disagreement between the two results* or the result of the review is uncertain, a second echocardiogram needs to be performed. This will be done by a Consultant Paediatric Cardiologist at Birmingham Children's Hospital

Date of second echocardiography ___ / ___ / ___

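### Distress in all false-positive parents is read as caused by the false alarm, although some of their babies are expected to have real non-cardiac illness

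*Protocol*

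**What the plan says.** Section 5.3.2 offers the acceptability questionnaire to parents of every screen-positive baby, to parents of false negatives, and to a sample of parents of true negatives. The four groups are defined by PO result and presence of CHD alone. Having all four is said to allow the effect of being screened to be told apart from the effect of the screening outcome.

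Section 5.3.2.2 notes that the literature on false positives conflicts: some work finds lasting effects, while other work "suggests the high levels of anxiety are dispelled by diagnostic tests showing the baby is healthy". It therefore assesses false-positive parents soon after testing and at one year, adds a bonding questionnaire both times, and concludes: "This will give us an indication of both the degree and duration of distress caused by the outcome".

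Elsewhere the protocol allows for illness in babies without CHD. Section 4.1 includes an oxygen test to look for respiratory causes of persistently low readings. Appendix D, Section 9, asks "Did this baby have a respiratory illness or any illness other than CHD", and Section 12 records days on the neonatal unit. No text links these items to the distress analysis. The explanatory variables named in 5.3.2.1 are illness perceptions of CHD and optimism.

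**The concern.** The conflict in the literature that 5.3.2.2 wants to address is whether distress persists once the baby is shown to be well. Only parents of babies in whom nothing was found can answer that. The false-positive group as defined also takes in babies with respiratory disease or another non-cardiac illness. Lasting distress or altered bonding in the pooled group could then come from the alarm, from the baby's illness, or from both, and the planned grouping cannot tell which. For some of these families PO will have found something useful, and their distress would still be reported as harm from a false alarm.

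The edge of the group is also loose. Section 5.3.2 speaks of CHD without qualification, while the accuracy objective in 1.3 concerns critical and serious CHD. A screen-positive baby with a lesser lesion is a true positive on one reading and a false positive on the other. Section 1.2.1 lists as unstudied the "psychosocial impact of false positive results or identification of non critical CHD", naming these as two things; the four groups do not separate them.

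**Working it through.** **Size of the group, from the plan's own figures.** Section 6.1: "the study aims to recruit a sample of 20,000 neonates". Section 4.3.1: "Given an assumed performance of 75% sensitivity and 99.5% specificity, and an overall prevalence of 5 per 1000".

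- Babies with CHD: 20,000 × 0.005 = 100; without: 19,900.
- True positives: 100 × 0.75 = 75.
- False positives: 19,900 × (1 − 0.995) = 99.5.
- Screen positives: 75 + 99.5 = 174.5, or 8.7 per 1000.
- Share with CHD: 75 / 174.5 = 43.0%.

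Section 4.3.1 states "we would expect 9 per 1000 to undergo echocardiography based on low saturation by PO or symptoms apparent at clinical examination" and that "between 40-50% of these will have clinically significant CHD". Both figures reproduce. False positives are 99.5 / 174.5 = 57% of screen positives. At a prevalence of 2 per 1000 their number hardly moves: 19,960 × 0.005 = 99.8. These are counts of babies; returned questionnaires may be fewer.

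**Direction of the bias.** Let f be the share of false positives with real non-cardiac illness, and d the extra distress of their parents, in SD units, over parents of well false positives. The pooled mean exceeds the mean for well false positives by f × d. This is upward whenever d is positive.

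**Illustration only.** The documents give neither f nor d. The values below are assumptions.

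| f | ill / well babies | shift, d = 0.5 | shift, d = 1.0 |
|---|---|---|---|
| 10% | 10 / 90 | 0.05 SD | 0.10 SD |
| 25% | 25 / 75 | 0.125 SD | 0.25 SD |
| 50% | 50 / 50 | 0.25 SD | 0.50 SD |

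The protocol does not give the size of the true-negative sample. With an assumed sample equal to the false positives, a two-sided 5% test, and no excess distress at all in parents of well false positives, the pooled comparison would still be significant about 14% of the time (f = 25%, d = 0.5), 39% (25%, 1.0) or 91% (50%, 1.0).

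**What a split can deliver.** Power to detect a 0.5 SD difference between parents of ill and well false positives is about 32%, 58% and 70% for f = 10%, 25% and 50%. The standard error of the mean in the no-disorder group rises by 1/√(1 − f): factors of 1.05, 1.15 and 1.41.

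**The case against.** The strongest reply is that PO is evaluated as a test for CHD, so a positive result without CHD is by definition a false positive, and the parent groups rightly follow the accuracy table. Sections 5.3.2 to 5.3.2.2 fix no model or contrast for distress, the list of explanatory variables is open-ended, and an analysis plan could add a split. That stands as far as it goes: the grouping is legitimate as an overall summary and nothing forbids a split. It does not remove the difficulty, because the grouping and the causal reading of it are both stated in the protocol.

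A reader might infer that the protocol assumes its own false positives are healthy. It does not: the remark about healthy babies reports one side of a literature the section itself calls contradictory. A reader might also take the false-positive results to be the study's main evidence of psychological harm. The documents do not say so; all four groups are assessed, and distress is also compared with population norms and other screening studies.

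Eligibility limits the share who are ill, since babies must be asymptomatic at birth and recorded as well on the form. Illness that emerges or is found later is not excluded, but the upper end of the assumed range has no support in the documents.

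Finally, splitting by diagnosis brings an asymmetry. Section 9 is completed only after an abnormal examination or a failed second reading, so true negatives cannot be filtered by the same item.

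**Conclusion.** The point holds as one of attribution. Read as written, distress from having a sick baby is pooled with distress from a false alarm, and the total is credited to the screening outcome. About 100 false positives are expected. The bias is upward if parents of ill babies are more distressed, but its size is unknown. The range of 0.05 to 0.50 SD above follows entirely from assumed inputs and should not be quoted as an estimate; its low end is negligible.

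The unclear boundary between true and false positives for lesser CHD is a separate, smaller ambiguity in the same groups. A reader might infer that the study's accuracy results are affected. They are not: this concerns a secondary outcome, and no primary accuracy estimate changes. It is a cheap improvement worth making.

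**What to change.** In 5.3.2 and 5.3.2.2:

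- Keep the overall false-positive result.
- Also report screen-positive parents by the baby's final diagnosis, using Appendix D Section 9, the echocardiography result and the Appendix E categories: critical or serious CHD, lesser CHD, non-cardiac illness, and no disorder found.
- Confine any statement about distress caused by a false alarm to the no-disorder group. Where that group is compared with true negatives, note that the latter could not be screened for illness in the same way.
- Describe the comparison between diagnostic groups as mainly descriptive.
- State which severity of CHD separates true from false positives for the parent groups.

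The cost is protocol wording and a regrouping of data already collected on every test-positive baby. The no-disorder group is smaller than the pooled group, so its interval is wider: by 5% to 41% for the group mean over the assumed illness shares.
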